### 2.2.3 *$^{68}\text{Ga}$ -OPS202 positive population*

All subjects who received  $^{68}\text{Ga}$ -OPS202 with at least one readable screening  $^{68}\text{Ga}$ -OPS202 PET, at least one readable screening ceCT scan, at least one readable screening  $^{18}\text{F}$ -FDG-PET scan, and have at least one lesion identified by central readers on screening  $^{68}\text{Ga}$ -OPS202 PET. This population encompasses subjects with ssTr2 positive lesion(s) (i.e., avid lesion with  $^{68}\text{Ga}$ -OPS202).

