### 2.2.4 *$^{68}\text{Ga}$ -OPS202 response evaluable population*

All subjects in the  $^{68}\text{Ga}$ -OPS202 positive population with the following 6 weeks post second  $^{177}\text{Lu}$ -OPS201 administration (second cycle): a readable  $^{68}\text{Ga}$ -OPS202 PET, a readable ceCT scan, and a readable  $^{18}\text{F}$ -FDG-PET scan.

The  $^{68}\text{Ga}$ -OPS202 positive and  $^{68}\text{Ga}$ -OPS202 response evaluable populations will be used for the analyses of diagnostic endpoints of  $^{68}\text{Ga}$ -OPS202.

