### 3.2.1.2 Diagnostic Sensitivity of $^{68}\text{Ga}$ -OPS202 (For Phase 1 and Phase 2):

a) Diagnostic sensitivity of  $^{68}\text{Ga}$ -OPS202 imaging at baseline using RECIST as the SOT by subject-based analysis. The SOT is the results on RECIST from the contrast enhanced CT (or contrast enhanced MRI) scan images performed 6 weeks after second  $^{177}\text{Lu}$ -OPS201 administration (second cycle). Complete response (CR), partial response (PR) and stable disease (SD) will be considered as positive response, while progressive disease (PD) will be considered as negative response.

Diagnostic sensitivity between  $^{68}\text{Ga}$ -OPS202 at baseline and SOT will be assessed using performance specified in Table 7.

Table 7 Diagnostic performance of  $^{68}\text{Ga}$ -OPS202 PET/CT compared to RECIST as the SOT

$^{68}\text{Ga}$ -OPS202 PET/CT scan results	SOT results (using RECIST)	
	Positive (CR + PR + SD) 6 weeks post 2nd $^{177}\text{Lu}$ OPS201	Negative (PD) 6 weeks post 2nd $^{177}\text{Lu}$ OPS201
Subjects with lesions detected by $^{68}\text{Ga}$ -OPS202 at baseline	Positive Response	Negative Response

SAP Final: Version 2.0: [03 January 2020]

40/57

The sensitivity corresponds to the probability of positive response from  $^{177}\text{Lu}$ -OPS201 based on lesions identified with ceCT (or ceMRI). Sensitivity will be computed using following formula, for overall subjects (subject-based approach):

$$Sensitivity = \frac{Positive\ Response}{Positive\ Response + Negative\ Response}$$

For Phase 1 subjects only, the above analysis will be repeated using volumetric RECIST as SOT.

b) Diagnostic sensitivity of  $^{68}\text{Ga}$ -OPS202 imaging at baseline using mGa-RECIST as the SOT by subject-based analysis. The SOT is the results from mGa-RECIST from the contrast enhanced CT (or contrast enhanced MRI) scan images performed 6 weeks after second  $^{177}\text{Lu}$ -OPS201 administration (second cycle). Complete response (CR), partial response (PR) and stable disease (SD) will be considered as positive response, while progressive disease (PD) will be considered as negative response.

Diagnostic sensitivity between  $^{68}\text{Ga}$ -OPS202 at baseline and SOT will be assessed using performance specified in Table 8.

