**Table 8 Diagnostic performance of  $^{68}\text{Ga}$ -OPS202 PET/CT compared to mGa-RECIST\* as the SOT**

$^{68}\text{Ga}$ -OPS202 PET/CT scan results	SOT results (using mGa-RECIST)	
	Positive (CR + PR + SD) 6 weeks post 2nd $^{177}\text{Lu}$ OPS201	Negative (PD) 6 weeks post 2nd $^{177}\text{Lu}$ OPS201
Subjects with lesions detected by $^{68}\text{Ga}$ -OPS202 PET/CT at baseline	Positive Response	Negative Response

\*modified Ga-RECIST using RECIST criteria on only those lesions which are  $^{68}\text{Ga}$ -OPS202 avid at baseline

The sensitivity corresponds to the probability of positive response from  $^{177}\text{Lu}$ -OPS201 based on lesions identified with  $^{68}\text{Ga}$ -OPS202-PET/ceCT (or ceMRI). Sensitivity will be computed using following formula, for overall subjects (subject-based approach):

$$Sensitivity = \frac{Positive\ Response}{Positive\ Response + Negative\ Response}$$

For Phase 1 subjects only, the above analysis will be repeated using volumetric mGa-RECIST as SOT.

c) Diagnostic sensitivity of  $^{68}\text{Ga}$ -OPS202 imaging at baseline by subject-based, organ-based and lesion-based analysis compared to standard-of-truth (SOT). The SOT is the contrast enhanced CT (or contrast enhanced MRI) scan images acquired at baseline.

Diagnostic sensitivity between  $^{68}\text{Ga}$ -OPS202 at baseline and SOT at baseline will be assessed using performance specified in Table 9.

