**Table 9 Diagnostic performance of  $^{68}\text{Ga}$ -OPS202 PET/CT compared to SOT of ceCT (or ceMRI)**

$^{68}\text{Ga}$ -OPS202 PET/CT scan results	SOT results (ceCT/ceMRI)	
	Lesions detected at baseline	Lesions not detected at baseline
Lesions detected at baseline	True Positive (TP)	False Positive (FP)
Lesions not detected at baseline	False Negative (FN)	True Negative (TN)* [will remain unknown]

\*True negative will remain unknown at the lesion level

The sensitivity corresponds to the probability that the  $^{68}\text{Ga}$ -OPS202 scan at baseline detects the lesions, given that the lesions are detected (positive) by SOT at baseline. This measurement refers to the ability of the test to correctly identify those lesions with the outcome of interest. Sensitivity is defined as the proportion of lesions with a positive ‘standard’ test response who also have a positive ‘experimental’ test response.

For each assessment, the sensitivity will be computed using following formula, for each subject, for each organ and overall lesions:

$$\text{Sensitivity} = \frac{TP}{TP + FN}$$

d) Diagnostic sensitivity of  $^{68}\text{Ga}$ -OPS202 imaging at baseline by both organ-based and lesion-based analysis compared to the SOT of  $^{177}\text{Lu}$ -OPS201 SPECT/CT after first administration. The contrast enhanced CT (or contrast enhanced MRI) scan images acquired at baseline will be used for anatomical location and lesion mapping between the two imaging techniques.

Diagnostic sensitivity between  $^{68}\text{Ga}$ -OPS202 at baseline and  $^{177}\text{Lu}$ -OPS201 SPECT/CT as SOT will be assessed using performance specified in Table 10.

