**Table 10 Diagnostic performance of  $^{68}\text{Ga}$ -OPS202 compared to SOT of  $^{177}\text{Lu}$ -OPS201 SPECT/CT**

$^{68}\text{Ga}$ -OPS202 scan results	SOT results ( $^{177}\text{Lu}$ -OPS201 SPECT/CT)	
	Lesions detected after first administration of $^{177}\text{Lu}$ -OPS201	Lesions not detected after first administration of $^{177}\text{Lu}$ -OPS201
Lesions detected at baseline	True Positive (TP)	False Positive (FP)
Lesions not detected at baseline	False Negative (FN)	True Negative (TN) [will remain unknown]*

\*True negative will remain unknown at the lesion level

The sensitivity corresponds to the probability that the  $^{68}\text{Ga}$ -OPS202 detects the lesion identified on the  $^{177}\text{Lu}$ -OPS201 SPECT/CT scan after first administration. This measurement refers to the ability of the test to correctly identify those lesions with the outcome of interest. Sensitivity is defined as the proportion of lesions with a positive ‘standard’ test response who also have a positive ‘experimental’ test response.

For each assessment, the sensitivity will be computed using following formula, for each organ and overall lesions:

$$\text{Sensitivity} = \frac{TP}{TP + FN}$$

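### Sensitivity of 68Ga-OPS202 against ceCT/ceMRI is computed only in scan-positive subjects, which overstates it; analyses a) and b) call a disease-control proportion sensitivity

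*SAP*

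**What the plan says.** Section 2.2.3 defines the 68Ga-OPS202 positive population. Besides readable screening images, subjects must "have at least one lesion identified by central readers on screening" 68Ga-OPS202 PET. Section 2.2.4 takes a subset of that population with readable scans after the second 177Lu-OPS201 administration. It then states that the positive and "response evaluable populations will be used for the analyses of diagnostic endpoints of" 68Ga-OPS202. No set of all scanned subjects is named for these endpoints.

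Section 3.2.1.2 describes four analyses, each called diagnostic sensitivity:

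- **a) and b), Tables 7 and 8.** The standard of truth is RECIST or mGa-RECIST 6 weeks after the second administration. CR, PR and "stable disease (SD) will be considered as positive response, while progressive disease (PD) will be considered as negative response". Each table has one test row, for subjects with lesions detected at baseline. The formula is positive responses over positive plus negative responses, and the text explains it thus: "The sensitivity corresponds to the probability of positive response from" 177Lu-OPS201.
- **c), Table 9.** The standard of truth is baseline ceCT or ceMRI. Sensitivity is the probability that the scan detects the lesions, "given that the lesions are detected (positive) by SOT at baseline", computed as TP/(TP+FN). For levels of analysis the SAP says that "the sensitivity will be computed using following formula, for each subject, for each organ and overall lesions".
- **d), Table 10.** The same TP/(TP+FN) formula, with 177Lu-OPS201 SPECT/CT after the first administration as the standard of truth.

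**The concern.** Sensitivity asks how often the test is positive when the reference is positive. In c) the test result decides who is analysed: a subject whose ceCT shows lesions and whose 68Ga-OPS202 PET shows none is excluded before counting starts. Those are the subjects in whom the scan misses every lesion. The SAP expects scan-negative subjects, since section 1.2.1 has a rule for consecutive screening failures on a negative PET. Reported without qualification, c) would overstate the share of ceCT/ceMRI lesions that the scan shows.

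Analyses a) and b) have a different fault. They start from a positive test and read off treatment outcome, so they say nothing about missed lesions and change with treatment results and with who stays on treatment. Section 3.2.1.2 therefore uses one word for two incompatible quantities.

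**Working it through.** The SAP states no expected sensitivity, target or sample size for these analyses, so there is no figure of its own to reproduce. All numerical values of g, s, k and the subject counts below are assumptions.

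**Analysis c).** Let L be the number of ceCT/ceMRI lesions in all scanned subjects, g the share of them in subjects with no lesion on 68Ga-OPS202 PET, and s the value of TP/(TP+FN) in scan-positive subjects.

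- Scan-positive subjects: TP = s(1-g)L and FN = (1-s)(1-g)L. The planned analysis reports s.
- Scan-negative subjects: TP = 0 and FN = gL. The planned analysis omits them.
- All scanned subjects: sensitivity = s(1-g)L / L = s(1-g).
- Overstatement factor: s / [s(1-g)] = 1/(1-g).

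With s = 80%:

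| g | Reported | All scanned subjects | Factor |
|---|---|---|---|
| 5% | 80% | 76% | 1.05 |
| 10% | 80% | 72% | 1.11 |
| 20% | 80% | 64% | 1.25 |
| 30% | 80% | 56% | 1.43 |

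The screening numbers in section 1.2.1 (about 340 scanned for 172 enrolled in Phase II) do not supply g. They count subjects, not lesions, and treatment also requires two avid lesions of at least 20 mm and at least 50% matching with FDG-PET.

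The subject-based version depends on a rule that the SAP does not state outright. If it is the proportion of a subject's lesions that are detected, which Table 9's lesion cells suggest, the result is inflated but not forced to 100%. If any detected lesion counts as detection, it is close to 100% by construction.

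**Analyses a) and b).** The formula is (CR+PR+SD)/(CR+PR+SD+PD) among scan-positive subjects. That is P(disease control | test positive), the form of a predictive value. Sensitivity would need the scan-negative row that Tables 7 and 8 lack.

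Nor is it the plan's DCR, which uses best overall response (sections 3.1.2 and 1.3.2.1). In Phase II a subject with PD at the first scan counts in the DCR denominator, because one post-baseline assessment is enough for the PP population (section 2.2.2). That subject generally has no scan after a second administration, since radiological progression ends treatment (section 1.3.2.10). Exceptions are possible because the site read manages the subject while the central read determines efficacy (section 1.3.2.1, Phase II).

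Illustration for Phase II with 100 scan-positive treated subjects:

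- 20 have central PD at the first scan.
- 24 have SD or better at the first scan, then PD at the second.
- 56 have SD or better at both.

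Let k be the share of the 20 who still receive the second administration and have the later scan, and suppose that the other 80 all have a usable later scan. The Table 7 value is 56/(80+20k):

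| k | Table 7 value | Best-response DCR |
|---|---|---|
| 0 | 56/80 = 70.0% | 80/100 = 80% |
| 0.25 | 56/85 = 65.9% | 80% |
| 0.5 | 56/90 = 62.2% | 80% |
| 1 | 56/100 = 56.0% | 80% |

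The figure called sensitivity moves by 14 percentage points while every baseline scan result stays the same. For Phase I the comparison with DCR is less clear, because section 1.3.2.1 limits response evaluability to subjects who reached the end of Cycle 2 while section 3.2.1.1 names the wider MTCA evaluable population.

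**The case against.** The strongest reply is that 68Ga-OPS202 images sstr2 expression. A wholly scan-negative subject may have sstr2-negative tumour rather than missed lesions, and section 2.2.3 openly fixes a scan-positive population. On that view c) is a legitimate conditional estimate and only its label is loose. This stands in part: a conditional value may be reported. But the definition given for c) conditions only on the standard of truth, and no label or denominator tells the reader otherwise. Section 3.2.14 allows a denominator footnote but does not require one here.

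It can also be said that a) and b) state openly what they compute, so that only the name is wrong. That is correct, and renaming is all that is asked. The name still matters, because the same section uses it for TP/(TP+FN).

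Some information on scan-negative subjects would survive. Phase II has an endpoint for the proportion of subjects with sstr2-positive lesions, and section 5 keeps a listing of screening failures. Neither is attached to the sensitivity estimate, and Phase I has no such endpoint.

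Finally, the magnitudes are assumed, and the practical consequence is small. Both points stand.

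**Conclusion.** The concern holds on both parts, as a minor point. In c) the direction of the bias is certain whenever any scanned subject has ceCT/ceMRI lesions and none on 68Ga-OPS202 PET. It applies whichever of the two populations is used, because one is nested in the other. Its size cannot be determined from the SAP: the factor 1/(1-g) runs from 1.05 to 1.43 over the assumed range of g. The upward bias is relative to the SAP's own unconditional definition; as a value for scan-positive subjects only, the estimate would be sound if so labelled. Analyses a) and b) are disease-control proportions under the wrong name.

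The weight is small because no target, test or decision rule depends on these estimates. After premature closure, section 5 reduces the Clinical Study Report to listings, none of them diagnostic. Section 5 does not, however, withdraw sections 2.2.3, 2.2.4 or 3.2.1.2, so their status is left open.

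**What to change.** - **c)** Use all subjects with a readable screening 68Ga-OPS202 PET and a readable baseline ceCT/ceMRI, whatever the PET result, and count unmatched ceCT/ceMRI findings as FN. The readable FDG-PET condition can be dropped, since c) does not use FDG. State the subject-level rule: within-subject lesion proportion, or at least one matched lesion.
- **Fallback for c)** If central ceCT/ceMRI lesion counts do not exist for scan-negative subjects, label the estimate *conditional on 68Ga-OPS202-positive subjects*. Report beside it, in both phases, how many scanned subjects were excluded as scan-negative.
- **a) and b)** Rename to *proportion with disease control 6 weeks after the second administration among 68Ga-OPS202-positive subjects*. Report how many scan-positive treated subjects had no such scan, and why.
- **d)** State that it is conditional on treated, scan-positive subjects.
- **Section 5** State whether section 3.2.1.2 is still to be performed.

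The cost is SAP wording and table shells. The preferred version of c) also needs a central lesion count on baseline ceCT/ceMRI in scan-negative subjects, which the SAP does not confirm. It will give a less favourable figure, in a population different from that of a), b) and d). The fallback needs only a label and a count.

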### 2.2.4 *$^{68}\text{Ga}$ -OPS202 response evaluable population*

All subjects in the  $^{68}\text{Ga}$ -OPS202 positive population with the following 6 weeks post second  $^{177}\text{Lu}$ -OPS201 administration (second cycle): a readable  $^{68}\text{Ga}$ -OPS202 PET, a readable ceCT scan, and a readable  $^{18}\text{F}$ -FDG-PET scan.

The  $^{68}\text{Ga}$ -OPS202 positive and  $^{68}\text{Ga}$ -OPS202 response evaluable populations will be used for the analyses of diagnostic endpoints of  $^{68}\text{Ga}$ -OPS202.

## 2.3 Safety

Safety population is all subjects who received at least one dose of  $^{177}\text{Lu}$ -OPS201 or  $^{68}\text{Ga}$ -OPS202.

- $^{68}\text{Ga}$ -OPS202 safety population: All subjects who received at least one dose of  $^{68}\text{Ga}$ -OPS202.
- $^{177}\text{Lu}$ -OPS201 safety population: All subjects who received at least one dose of  $^{177}\text{Lu}$ -OPS201.

## 2.4 MTCA evaluable population

MTCA evaluable population is all subjects who received at least one dose of  $^{177}\text{Lu}$ -OPS201 in the radioactivity escalation of the phase I of the study. The MTCA-evaluable population will be used to determine the MTCA/MTSA/MACA for phase I of the study.

## 2.5 Dosimetry

### 2.5.1 *Dosimetry population*

All subjects who received at least one dose of  $^{177}\text{Lu}$ -OPS201 for whom at least one complete set of dosimetry imaging and dosimetry blood sample measurements is available. Dosimetry may be analysed separately for phase I and phase II.

### 2.5.2 *Per protocol dosimetry population*

All subjects in the dosimetry population for whom no major protocol violations occurred affecting dosimetry variables. Dosimetry may be analysed separately for phase I and phase II.

## 2.6 Pharmacokinetics

### 2.6.1 Radiopharmaceutical pharmacokinetic population

All subjects who received at least one dose of  $^{177}\text{Lu}$ -OPS201 and have at least one measured radioactive concentration in blood. Radiopharmaceutical PK may be analysed separately for phase I and phase II.

### 2.6.2 OPS201 pharmacokinetic population

All subjects who received at least one dose of  $^{177}\text{Lu}$ -OPS201 and have no major protocol deviations affecting the PK variables and who have a sufficient number of OPS201 concentrations to estimate the main PK parameters (i.e. maximum observed concentration ( $C_{\max}$ ), time to maximum observed drug concentration ( $t_{\max}$ ) and area under curve (AUC)). OPS201 PK may be analysed separately for phase I and phase II.

## 2.7 Primary population

For the phase I of the study, the primary analysis based on the primary safety endpoint will be performed on the MTCA evaluable population.

For the phase II of the study, the primary analysis based on the primary efficacy endpoint will be performed on the PP population. In addition, secondary/confirmatory analysis may be performed on the ITT population.

The primary dosimetry analysis will be based on the dosimetry population. A supportive analysis will be based on per protocol dosimetry population.

The assessment of safety and tolerability will be based on the safety population.

The assessment of PK will be based on the radiopharmaceutical pharmacokinetic population and OPS201 pharmacokinetic population.

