#### Sample Size Determination for Phase II

The sample size is calculated using Simon's optimal two-stage design based on the ORR rate (complete response (CR) + partial response (PR)) following  $^{177}\text{Lu}$ -OPS201 treatment.

For the Simon's optimal two-stage design, the hypotheses that will be tested for each cohort are:  $H_0: \text{ORR} \leq \text{ORR}_0$  versus the alternative  $H_1: \text{ORR} > \text{ORR}_0$  where ORR is the true objective response rate following  $^{177}\text{Lu}$ -OPS201 treatment that warrants further clinical development, and  $\text{ORR}_0$  is the minimum objective response rate to be excluded from further clinical development. The thresholds for ORR and  $\text{ORR}_0$  may be updated based on results from phase I and the advances in scientific knowledge.

ORR will be analysed at the end of Stage 1 (6 weeks after the second  $^{177}\text{Lu}$ -OPS201 administration (Cycle 2) of the core treatment period of the last evaluable subject of the Stage 1 cohort for each type of cancer). If the observed number of responders is below a predefined threshold, the respective study cohort will be stopped for futility. Otherwise, additional subjects will be treated to complete the planned enrolment. At the end of Stage 2, the null hypothesis will be rejected depending on the total observed number of responders based on a predefined threshold.

For the SCLC cohort, with 69 response evaluable subjects, there will be 90% power to test a null hypothesis ORR rate of 23% and an alternative hypothesis ORR rate of 40% at one-sided significance level of  $\alpha=0.05$ . The first stage consists of 29 subjects. If seven responses or less are seen in the first 29 subjects then the trial is stopped. Otherwise accrual continues to a total of 69 response evaluable subjects. Approximately 76 subjects are planned to be enrolled to account for 10% study dropout.

For the BC cohort, with 87 response evaluable subjects, there will be 90% power to test a null hypothesis ORR rate of 12% and an alternative hypothesis ORR rate of 25% at one-sided significance level of  $\alpha=0.05$ . The first stage consists of 33 subjects. If four responses or less are seen in the first 33 subjects then the trial is stopped. Otherwise accrual continues to a total of 87 response evaluable subjects. Approximately 96 subjects are planned to account for 10% study dropout.

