### 2.2.2 *Per Protocol population (PP)*

All subjects in the ITT population in the phase II of the study who have measurable disease at baseline, have at least one post baseline response assessment and no major protocol deviations occurred that could affect efficacy analysis.

The PP population will be used for the analyses of ORR, DCR, PFS, OS, TTP, TTR and DoR.

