## 2.8 Reasons for exclusion from the analyses

Any major protocol deviation will be described and its impact on inclusion in each analysis population for any subject will be specified. The final list of protocol deviations impacting each analysis population will be reviewed prior to interim analysis and database lock. The list may be updated, up to the point of interim analysis and database lock, to include any additional major protocol deviations impacting inclusion in each analysis population.

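### The Phase II primary ORR test leaves out treated subjects who were never scanned, so its nominal 5% error rate does not hold for treated patients

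*SAP*

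**What the plan says.** Section 2.7 fixes the deciding set: "For the phase II of the study, the primary analysis based on the primary efficacy endpoint will be performed on the PP population". Section 2.2.1 defines ITT for Phase II as everyone given at least one dose of the therapeutic product. Section 2.2.2 narrows this to PP: subjects must have measurable disease at baseline and "have at least one post baseline response assessment and no major protocol deviations occurred that could affect efficacy analysis". Section 2.8 says of the deviations that exclude subjects: "The list may be updated, up to the point of interim analysis and database lock". Section 3.2.4.1 rules out imputation and uses observed data only. Appendix 1, item 16, deals with a missed assessment that is followed by a later one, not with a subject who has none.

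The test is in section 1.3.4. Each cohort has a Simon optimal two-stage design at one-sided 5% and 90% power, with accrual running to 69 (SCLC) and 87 (BC) response-evaluable subjects. At the end of stage 2, "the null hypothesis will be rejected depending on the total observed number of responders based on a predefined threshold". No final number is given.

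Three related statements do not agree:

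- **Evaluable numbers.** Section 1.3.4 gives 69 and 87 as response evaluable and 76 and 96 as planned enrolment. Section 1.2.1 calls 76 and 96 the required evaluable numbers.
- **Meaning of response evaluable.** In Phase II the term is not tied to any analysis set.
- **Status of ITT.** Section 2.7 says that "secondary/confirmatory analysis may be performed on the ITT population". Sections 3.2.1.1 and 3.2.8 say that ITT will be used alongside PP.

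**The concern.** This is a single-arm comparison with a fixed null. No control arm undergoes the same exclusions, so they cannot cancel. A treated subject who dies or withdraws before any scan cannot have a documented response. Leaving that subject out removes a certain non-responder from the denominator and nothing from the numerator. The PP response rate then exceeds the treated-patient rate, and both Simon looks are judged on the higher rate.

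Two things are at stake. The cohort may be declared promising when the treatment does no better than the null in the patients who received it. The futility look may also let through a cohort it was meant to stop. The deviation exclusions add uncertainty of unknown direction, because they may remove responders as well as non-responders.

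**Working it through.** **Inputs (sections 1.3.4 and 3.2.16).**

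- SCLC: null p0 = 0.23, alternative p1 = 0.40. Stage 1 has 29 subjects, stopping at 7 or fewer responses. Total 69.
- BC: p0 = 0.12, p1 = 0.25. Stage 1 has 33 subjects, stopping at 4 or fewer. Total 87.
- Both: one-sided alpha 0.05, power 90%.

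**Formula.** With n1 and r1 the stage 1 size and stopping limit, n the total, and r the largest final count that does not reject:

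P(reject | p) = Σ over x1 > r1 of Bin(x1; n1, p) × P(X2 > r − x1), where X2 ~ Bin(n − n1, p).

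**Step 1: reproduce the plan.** A search for the design with the smallest expected sample size under the null returns the SAP's sizes and supplies the final counts it omits.

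| Cohort | Design (r1/n1, r/n) | Reject at | Alpha | Power | Early termination |
|---|---|---|---|---|---|
| SCLC | 7/29, 21/69 | 22 or more | 4.97% | 90.0% | 0.6555 |
| BC | 4/33, 15/87 | 16 or more | 4.58% | 90.4% | 0.6374 |

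The early-termination probabilities match section 3.2.16.

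**Step 2: remove unscanned subjects.** Let d be the share of treated subjects with no post-baseline assessment. The SAP does not give d, so it is an assumption. All responders stay in PP, so when the treated-patient ORR is p0 the PP rate is p0/(1 − d). At d = 10% this is 0.23/0.90 = 25.6% and 0.12/0.90 = 13.3%. PP is taken to reach 69 or 87, as the accrual rule implies.

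| d | SCLC PP rate | SCLC P(reject) | BC PP rate | BC P(reject) |
|---|---|---|---|---|
| 0% | 23.0% | 4.97% | 12.0% | 4.58% |
| 2% | 23.5% | 6.0% | 12.2% | 5.3% |
| 5% | 24.2% | 8.0% | 12.6% | 6.7% |
| 10% | 25.6% | 12.6% | 13.3% | 9.7% |

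The chance of passing the futility look under the same null rises from 34% to 47% (SCLC) and from 36% to 45% (BC) at d = 10%.

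**Step 3: test the all-treated alternative.** With every treated subject in the denominator and no scan counted as non-response, the response rate under the null is p0 again. The rules 22/69 and 16/87 then return to 4.97% and 4.58%. If 76 and 96 are treated, the smallest final counts that keep alpha at or below 5% are:

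- SCLC: 24 or more of 76, alpha 4.6%, power 90.9%. At 23, alpha is 7.1%.
- BC: 18 or more of 96, alpha 3.1%, power 90.1%. At 17, alpha is 5.3%.

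**The case against.** **Premature closure.** Section 5 replaces the report's analyses with listings, none of them an efficacy output. Under this SAP version no PP test will be run. This stands, and it lowers the severity.

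**The 10% case is not an expected value.** Section 1.3.4 speaks of study dropout among enrolled subjects, and section 1.3.1 places enrolment at confirmation of eligibility, before dosing. Subjects never dosed are outside ITT as well and create no gap between the two sets. Sections 1.3.2.1 and 3.1.1 also provide for assessment at first clinical signs of progression, so some deteriorating subjects are scanned, stay in PP and count as non-responders. Both points stand. A reader might take 12.6% and 9.7% as the actual error rates; the documents support them only as an upper case.

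**PP size.** A reader might infer that PP is simply whatever remains of 76 or 96 enrolled, so that alpha drifts with its size, reaching 10.4% if 22 responders were still enough at 76 in SCLC. The documents do not support this. Sections 1.3.4 and 3.2.16 continue accrual to 69 and 87 response-evaluable subjects. Nothing says that a final count, which the SAP never states, would be carried unchanged to another size. What remains is the conflict with section 1.2.1 and the undefined term.

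**ITT is not absent.** A reader of section 2.7 alone might conclude that an ITT analysis is only optional. Section 3.2.1.1 names both sets, and section 3.2.8 commits to comparing ITT and PP results for the primary efficacy analysis. But neither makes ITT the deciding set.

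**Safeguards.** Section 3.1.2 provides blinded independent readers, and section 2.8 has the deviation list reviewed before the interim analysis and database lock. These limit discretion but do not bring unscanned subjects back.

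**Conclusion.** The point holds. The 5% level is valid for PP subjects at exactly 69 and 87, but not for treated patients once any appreciable share is unscanned. The level is passed at d of about 0.06% in SCLC and 1.2% in BC, because the designs have little or no slack.

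The size of the excess depends on d and on unscanned subjects being non-responders. The second follows from the endpoint; the first is unknown. At a modest 2% to 5%, the error is 6.0% to 8.0% (SCLC) and 5.3% to 6.7% (BC). No size or direction is claimed for the deviation exclusions.

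Severity is moderate. The choice of set is a real defect in the plan's only formal efficacy test, and it is cheap to correct. It does not affect the listings to which section 5 confines the report.

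**What to change.** 1. In section 2.7, make the all-treated (ITT) set primary for ORR at both Simon looks and PP supportive. Count a treated subject with no post-baseline response assessment as a non-responder, and state this as an exception to section 3.2.4.1.
2. In sections 1.3.4 and 3.2.16, define stage 1 as the first 29 (SCLC) and 33 (BC) subjects treated, by date of first dose, with the stated stage 1 cut-offs unchanged.
3. State the final cut-off as a rule: the smallest responder count that keeps exact two-stage alpha at or below 5% for the number actually treated. Examples are 22/69 or 24/76 for SCLC, and 16/87 or 18/96 for BC. Fixed counts alone would not cover a different treated number.
4. Tie response evaluable to a named set, reconcile the evaluable numbers in section 1.2.1 with section 1.3.4, and align section 2.7 with sections 3.2.1.1 and 3.2.8 on whether ITT is performed.

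**Cost.** SAP wording only; no subjects beyond the 76 and 96 already planned. The downside is power. If 40% and 25% were meant for scanned subjects only and 10% of treated subjects are unscanned, the treated-patient rates are 0.40 × 0.90 = 36% and 0.25 × 0.90 = 22.5%. Power on 76 and 96 treated then falls to about 76% and 79%. The sponsor should say which population the alternatives describe.
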